**5.2.7 Analysis of Efficacy Outcomes for Antithrombotic Randomization by Pantoprazole Treatment Groups**

Subjects not randomized to pantoprazole/placebo were not followed up from the termination of the antithrombotic portion of the COMPASS study until the initiation of COMPASS LTOLE. Only subjects of the pantoprazole ITT analysis set were to be followed up until the Final pantoprazole/placebo Follow-up Visit, mainly to evaluate pantoprazole related outcomes.

Efficacy outcomes defined to analyze the objectives of the antithrombotic randomization in ITT data scope for CDB2 (i.e., up until the Final pantoprazole/placebo Follow-up Visit) will be reported by means of frequency tables only based on the pantoprazole ITT analysis set, by pantoprazole treatment groups, as suggested in the following example.

Table: Number of subjects with primary efficacy event and its components in ITT data scope for CDB2 (pantoprazole ITT analysis set)			
	Pantoprazole 40 mg od N=xxxx (100%)	Pantoprazole placebo od N=xxxx (100%)	Total N= xxxx (100%)
MI, stroke, or CV death	xxx ( xx.x%)	xxx ( xx.x%)	xxx ( xx.x%)

MI	xxx ( xx.x%)	xxx ( xx.x%)	xxx ( xx.x%)
Stroke	xxx ( xx.x%)	xxx ( xx.x%)	xxx ( xx.x%)
CV death	xxx ( xx.x%)	xxx ( xx.x%)	xxx ( xx.x%)
Footnotes:			
-	Only events that occurred in ITT data scope for CDB2 are taken into account.		
-	The events presented were efficacy events with respect to antithrombotic randomization. Antithrombotic study medication was to be stopped with Final Rivaroxaban/Aspirin Follow-up Visit. Hence, the randomized antithrombotic study medication was not to be taken for about one year during pantoprazole/placebo follow-up.		

### **5.3 Pharmacokinetics/Pharmacodynamics**

Not applicable.

### **5.4 Safety**

#### **5.4.1 Safety Outcome Events for the Antithrombotic Randomization**

Safety outcomes defined to analyze the objectives of the antithrombotic randomization in ITT data scope for CDB2 will be reported by means of frequency tables only based on the pantoprazole ITT analysis set, by pantoprazole treatment groups, as described in Section 5.2.7. These tables will be provided similarly to but separate from summaries of AE data.

The following safety events and their composites will be tabularized:

- Modified ISTH major bleeding
  - Fatal
  - Critical organ bleeding (non-fatal)
  - Requiring re-operation (non-fatal and non- critical organ)
  - Hospitalization (non-fatal, non-critical organ, not leading to re-operation)
  - Hospitalization where admission date < discharge date
  - Hospitalization where admission date = discharge date
  - Gastrointestinal
  - Gastrointestinal (excl. oral cavity and esophagus)
  - Intracranial
- Minor bleeding
- Modified ISTH major bleeding by bleeding site

#### **5.4.2 Events of Special Interest for the Pantoprazole Randomization**

Other (adverse) events of special interest with respect to the pantoprazole/placebo randomization are

- Pneumonia
- Clostridium difficile infection
- Other enteric infections
- Fracture
- Gastric atrophy

- Chronic kidney disease
- Diabetes
- Chronic obstructive lung disease
- Dementia.

The number and crude incidence of subjects with such events since informed consent (as the CRF suggests) will be summarized. The binary response variables will be evaluated with logistic regression as suggested by the following SAS code:

```
PROC LOGISTIC DATA = <dataset>;
CLASS trtgrp stratum;
MODEL outcome (event='1') = trtgrp / CLODDS= WALD CLPARM= WALD ;
STRATA stratum;
RUN;

/*
where
dataset = name of sub-dataset including Pantoprazole ITT subjects (those
          subjects randomized to pantoprazole/placebo)
trtgrp   = variable coding randomized pantoprazole treatment group
          (0 = Pantoprazole placebo, 1 = Pantoprazole)
outcome = event indicator (0 = no event, 1 = event)
stratum  = variable for antithrombotic stratification factor (three levels)
*/
```

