## Run-in

The run-in period will occur during the 28 days prior to initiation of randomized study treatment, with the exception of subjects who are randomized after CABG surgery, who will not undergo a run-in phase. During run-in, eligible subjects who have signed informed consent and discontinued any antithrombotic therapy will receive rivaroxaban placebo bid and aspirin 100 mg od. Study pantoprazole or pantoprazole placebo will not be administered during the run-in period.

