  - (a) the subject did not attend his/her Final Follow-Up Visit before the common trial close-out date and
  - (b) the subject's date of last trial contact is after the common trial close-out date.

This will constitute a right-censored observation.

Other outcomes of interest for the pantoprazole randomization are:

- pneumonia, enteric infections, and bone fractures as well as new diagnosis of gastric atrophy, chronic kidney disease, diabetes, chronic obstructive lung disease, and dementia since randomization.

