## 2. Study Objectives

The main objective for the pantoprazole randomization is

- To determine whether pantoprazole 40 mg od compared with placebo reduces the risk of upper gastrointestinal bleeding, ulceration, or gastrointestinal obstruction or perforation in subjects with CAD or PAD receiving antithrombotic medications.

Other objectives for the pantoprazole randomization are:

- To determine the effect of pantoprazole 40 mg od compared with placebo on the risk of pneumonia, clostridium difficile (C. diff) and other enteric infections, bone fractures, and new diagnosis since randomization of gastric atrophy, chronic kidney disease, diabetes, chronic obstructive lung disease and dementia in subjects with CAD or PAD.
- To determine whether treatment with pantoprazole 40 mg od potentially modifies the effects of antithrombotic treatment on major cardiovascular outcomes or bleeding events. I.e. whether pantoprazole interacts with the treatment effects of rivaroxaban 2.5 mg bid/aspirin 100 mg od vs. aspirin 100 mg od in its impact on outcomes.
- To determine whether treatment with pantoprazole 40 mg od has an effect on premature discontinuation of antithrombotic study treatment.

For further details on study objectives, please refer to integrated [SAP](#), version 4.1.

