### 4.2.1 ITT data scope for CDB2

The ITT data scope for CDB2 is the primary data scope for analyses of CDB2 data.

For the ITT data scope for CDB2, only outcome events at or after the date of randomization up until Last Follow-up Date (see Section 6 for definition) will be considered for analysis.

For those subjects with documentation of an outcome event within the ITT data scope for CDB2, time (in days) from randomization to the first occurrence of the event will be derived as:

- o the date of the subject's first event – the randomization date + 1.

This will constitute an uncensored observation.

For those subjects without documentation of an outcome event within the ITT data scope for CDB2, time (in days) from randomization to the censoring date will be derived as:

- the subject's Last Follow-up Date – the randomization date + 1.

This will constitute a right-censored observation.

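### Pantoprazole events of special interest: counted from consent rather than from randomization, with the direction of the odds ratio left to a software default

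*SAP*

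**What the plan says.** Section 5.4.2 of the pantoprazole close-out SAP lists nine events: pneumonia, Clostridium difficile infection, other enteric infections, fracture, gastric atrophy, chronic kidney disease, diabetes, chronic obstructive lung disease and dementia. On the counting window it states: "The number and crude incidence of subjects with such events since informed consent (as the CRF suggests) will be summarized". It then proposes logistic regression of a yes/no outcome on treatment, stratified by antithrombotic arm. The code contains "CLASS trtgrp stratum" with no reference-level or parameterisation option, asks for Wald limits on both the odds ratio and the parameter, and codes treatment as "0 = Pantoprazole placebo, 1 = Pantoprazole".

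Other places start the clock at randomization:

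- Section 2 of the same SAP, the objective: "bone fractures, and new diagnosis since randomization of gastric atrophy, chronic kidney disease, diabetes, chronic obstructive lung disease and dementia". The contrast there is pantoprazole compared with placebo.
- SAP 4.1, Section 6.2.4.1, the outcome definition: "new diagnosis of gastric atrophy, chronic kidney disease, diabetes, chronic obstructive lung disease, and dementia since randomization".
- Close-out SAP, Section 4.2.1, the primary scope for this database, which admits "only outcome events at or after the date of randomization up until Last Follow-up Date".

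SAP 4.1, Section 3 (Run-in) adds: "Study pantoprazole or pantoprazole placebo will not be administered during the run-in period".

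**The concern.** There are two separate defects in one short section.

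**Window.** An event between consent and randomization cannot be an effect of study pantoprazole. Counting it answers a slightly different question from the objective. The next section, 5.4.3, summarises adverse events in the scope that starts at randomization, so one report would use two windows for overlapping conditions.

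**Direction.** Section 5.4.2 never says which way its odds ratio runs. The Cox model in Section 5.2.3 does: placebo is 0, pantoprazole is 1, and the hazard ratio is the exponential of the coefficient. If the logistic output runs the other way, a ratio below 1 favours pantoprazole in the efficacy tables and placebo in these tables.

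These outcomes matter because SAP 4.1, Section 8.2 (Modification 6) added them after observational studies had linked pantoprazole use to harm. A reader will look here for the randomized answer.

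**Working it through.** The plan gives no figure for this analysis, so there is none to reproduce. The sizes below come from its stated inputs and from labelled assumptions.

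**1. Dilution from the consent window**

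Inputs: d = 28 days of run-in (SAP 4.1, Section 3, Run-in); T = 3 to 4 years expected average treatment duration (SAP 4.1, Section 3), used here as the follow-up time. Assumptions: constant event rate, and consent at the start of run-in.

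Share of placebo-rate events before randomization = d / (d + T):

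- T = 3 × 365.25 = 1,095.75 days: 28 / 1,123.75 = 2.5%
- T = 4 × 365.25 = 1,461 days: 28 / 1,489 = 1.9%

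Observed risk ratio = (RR × T + d) / (T + d), with an assumed true RR of 1.50:

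- 3 years: (1,643.6 + 28) / 1,123.75 = 1.488
- 4 years: (2,191.5 + 28) / 1,489 = 1.491
- If follow-up were only 2 years, the share would be 3.7% and the ratio 1.482.

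**2. Direction and scale of the logistic output**

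Software premise: without options, a CLASS variable in PROC LOGISTIC gets effect coding with the last level as reference. With unformatted 0/1 values the last level is 1, pantoprazole. The covariate is then +1 for placebo and −1 for pantoprazole, and the odds ratio reported is exp(2β), level 0 versus level 1.

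Illustration: 16,440 subjects (SAP 4.1, Section 7) split 1:1 over three equal strata gives 16,440 / 6 = 2,740 per cell. Event rates are assumed. SAS was not run. The code was emulated by a logistic model with three stratum intercepts, which at these stratum sizes approximates the conditional fit.

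| Assumed rates, pantoprazole vs placebo | OR with placebo as reference (95% CI) | OR from the code as printed (95% CI) |
|---|---|---|
| 3.0% vs 2.0% | 1.51 (1.23–1.84) | 0.66 (0.54–0.81) |
| 4.5% vs 4.0% | 1.12 (0.97–1.31) | 0.89 (0.77–1.04) |
| 2.0% vs 3.0% | 0.66 (0.54–0.81) | 1.51 (1.23–1.84) |

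Hand check of the first row: 3% and 2% of 2,740 round to 82 and 55 events per cell, and (82/2,658) / (55/2,685) = 1.506. Its reciprocal is 0.664.

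For the same row the log odds ratio, placebo versus pantoprazole, is −0.409, while the effect-coded parameter is half of that, −0.205, with exp(−0.205) = 0.815. The parameter limits requested in the code therefore refer to half the log odds ratio. Exponentiating them gives neither 0.66 nor 1.51.

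The Cox code in Section 5.2.3 uses the 0/1 variable directly, without CLASS, so its hazard ratio is pantoprazole versus placebo.

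**The case against.** **On the window.** The SAP states its choice openly and gives a reason, the CRF. The CRF is not at hand, and dated counts may not be obtainable; a binary rather than a time-to-event analysis would fit that. In Section 2 the words on randomization attach grammatically to the five new diagnoses, not to pneumonia, enteric infections or fractures, and the sentence in SAP 4.1 is ambiguous. Pre-randomization events fall equally on both arms in expectation. All of this stands and keeps the point small. It does not remove it: for five outcomes the objective and the analysis differ in plain words, the primary data scope supports the randomization window for all nine, and citing the CRF explains the choice without reconciling it.

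**On the direction.** The point rests on a software default, not on a sentence in the SAP. A text format on the treatment variable could reverse the level order. The code is offered as a suggestion, programming instructions sit in a separate TLF document (SAP 4.1, Section 1), the output row would read 0 vs 1, and the p-value is the same either way. This also stands. What remains is that the section leaves the direction unstated, and its code, taken with its own coding, yields the reverse of the stated contrast.

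A reader might infer that a pantoprazole harm would be reported as a protection. The documents do not support that: the output is a labelled reciprocal, and misreading it takes a further slip. A reader might also infer a material bias from the consent window. The arithmetic does not support that either.

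**Conclusion.** Both defects are real, correctable and modest. The consent window departs from the objective, explicitly for five diagnoses and by the primary data scope for all nine. Under a constant rate it adds about 2% of events, non-differentially, and pulls a risk ratio of 1.50 to about 1.49. That figure may not describe subjects randomized after CABG: they have no run-in and may consent before surgery (SAP 4.1, Table 3-2 footnotes), so peri-operative events such as pneumonia could enter the count. The documents do not allow that share to be sized.

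The logistic code, with unformatted 0/1 coding and default settings, gives the odds ratio as placebo versus pantoprazole and parameter limits on half the log scale. Inference is unchanged. The risk is misreading or mis-tabulation beside hazard ratios that run the other way.

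**What to change.** 1. Replace the CLASS line with one that names placebo as the reference for treatment: `CLASS trtgrp (REF='0') / PARAM=REF;`, with REF set to the placebo label if a format is attached. State in Section 5.4.2 that the odds ratio is pantoprazole versus placebo.
2. Restrict the comparison to events on or after randomization where CRF dates allow. Where they do not, say that the since-consent count departs from the objective.

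The cost is one line of code and one sentence of text, with possibly slightly fewer events in the comparison. If tables have already been produced from the printed code, check the direction that they show.

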### 5.4.3 Adverse Events

Summaries of reported adverse events will be provided based on

- the pantoprazole ITT analysis set using the ITT data scope for CDB2 and,
- for CSR purpose only, the pantoprazole safety analysis set and the pantoprazole treatment emergent data scope

as outlined in Section 4.2. The remaining principles of adverse event analyses will be applied as specified in the [SAP](#), version 4.1.

### 5.4.4 Death

Please refer to Section 5.4.1.

### 5.4.5 Pregnancies

Please refer to SAP, version 4.1.

### 5.4.6 Vital Signs

Please refer to SAP, version 4.1.

### 5.4.7 Clinical Laboratory Tests

Please refer to SAP, version 4.1.

**5.5 Analysis of COMPASS MIND Study**

Will be reported separately.

**6. Definitions**

Pantoprazole ITT analysis set	The pantoprazole ITT analysis set comprises all subjects that have been randomized to pantoprazole 40mg or pantoprazole placebo.
Final pantoprazole/placebo Follow-up Visit	Final visit at the end of the pantoprazole/placebo follow-up of the COMPASS trial
Pantoprazole/placebo Washout Visit	For subjects who participate in COMPASS in countries that have not yet approved the protocol amendment no. 11 forming integrated protocol version 4.0, an End of Washout Telephone Visit (Washout Visit) is envisaged 30 days post Final pantoprazole/placebo Follow-up Visit.
Last rivaroxaban/aspirin Follow-up Date	
If consent was not withdrawn:
 
Last rivaroxaban/aspirin Follow-up Date
 
= first of
 
 
• date of death (if applicable)
 
• date of completed Final rivaroxaban/aspirin Follow-up visit (if applicable)
 
• max (dates of visits completed, event dates).
 
 
If consent was withdrawn:
 
Last rivaroxaban/aspirin Follow-up Date
 
= first of
 
 
• max (date of death, date of withdrawal, date of confirmed alive)
 
• date of completed Final rivaroxaban/aspirin Follow-up visit (if applicable).
 

Last pantoprazole/placebo Follow-up Date	
If consent was not withdrawn:
 
Last pantoprazole/placebo Follow-up Date
 
= first of
 
 
• date of death (if applicable)
 
• date of completed Final pantoprazole/placebo Follow-up visit (if applicable)
 

## Statistical Analysis Plan

	
 
• max (dates of visits completed, event dates).
 
 
If consent was withdrawn:
 
Last pantoprazole/placebo Follow-up Date
 
= first of
 
 
• max (date of death, date of withdrawal, date of confirmed alive)
 
• date of completed Final pantoprazole/placebo Follow-up visit (if applicable).
 

Last Follow-up Date	
If subject is in pantoprazole ITT set:
 
Last Follow-up Date = Last pantoprazole/placebo Follow-up Date
 
If subject is not randomized to pantoprazole/placebo:
 
Last Follow-up Date = Last rivaroxaban/aspirin Follow-up Date

## Abbreviations

AE	Adverse event
AUS/ISR/ZAF	Australia/Israel/South Africa
bid	Twice daily
CAD	Coronary artery disease
CDB	Clean database
CHD	Coronary heart disease
CI	Confidence interval
CLI	Chronic Limb Ischemia
COMPASS	Cardiovascular Outcomes for People using Anticoagulation Strategies
COMPASS LTOLE	COMPASS Long-term Open-Label Extension
CRF	Case report form (either paper or electronic)
CSR	Clinical study report
CV	Cardiovascular
DSMB	Data Safety Monitoring Board
eGFR	estimated glomerular filtration rate
GI	Gastrointestinal
Hb	Hemoglobin
ICH	International Conference on Harmonization
ISTH	International Society on Thrombosis and Haemostasis
ITT	Intention-to-treat
LTOLE	Long-Term Open-Label Extension (= COMPASS LTOLE)
MI	Myocardial infarction
od	Once daily
PAD	Peripheral artery disease
PPD	
PPI	Proton pump inhibitor
SAE	Serious adverse event
SAP	Statistical analysis plan
SAS	Statistical Analysis Software

## 1. Introduction

The COMPASS study is a randomized double-blind trial utilizing a 3 x 2 partial factorial design evaluating the efficacy and safety of:

- rivaroxaban 2.5 mg twice daily (bid) + aspirin 100 mg once daily (od) versus aspirin 100 mg od and
- rivaroxaban 5 mg bid versus aspirin 100 mg od

for the prevention of myocardial infarction, stroke, and cardiovascular death in patients with established CAD or PAD who are receiving standard prevention therapies. Details about the study, as well as the already specified and conducted analyses are described in the integrated clinical study protocol, Version 4.0, dated 12 September 2017, the integrated SAP, Version 4.1, dated 31 March 2017 and the SAP for PPI-specific analyses, Version 1.0, dated 09 May 2018.

On February 06, 2017 the Data Safety Monitoring Board (DSMB) for the COMPASS study recommended that the antithrombotic study treatment arms rivaroxaban 2.5 mg bid/aspirin 100 mg od, rivaroxaban 5 mg bid, and aspirin 100 mg od be stopped as soon as an orderly close-out of this portion of the COMPASS trial could be carried out based on results of the first formal interim analysis. The DSMB made no recommendations regarding early termination of the pantoprazole treatment arms of the study. The Steering Committee decided that the pantoprazole study treatment arms would continue.

The database (Clean Database 1, CDB1) underlying the CSR and the main publications is based on a cut-off date of July 22, 2017 and, at Bayer, the release date of the first clinical database on August 04, 2017. The results for the antithrombotic randomization have been analyzed and reported in the clinical study report (CSR, PH-39342) of the COMPASS study and multiple scientific publications. The corresponding statistical analyses comprise information up to the subjects' rivaroxaban/aspirin washout visits since these data are considered relevant to the antithrombotic study treatment arms.

Based on a further data cut-off on August 31, 2018 a second Clean Database (CDB2) has been released on September 21, 2018 underlying the CSR addendum (PH-40183) and summarizing the results focusing on the pantoprazole randomization.

After the early stop of the antithrombotic study treatment in the COMPASS study, the sponsor made rivaroxaban 2.5 mg bis + aspirin 100 mg od available early for COMPASS trial subjects as part of a Long-Term Open-Label Extension (COMPASS LTOLE; short: LTOLE). Subjects who participated in the COMPASS study were invited to join LTOLE, and eligible subjects who agreed to participate were treated with the combination of rivaroxaban 2.5 mg bid/aspirin 100 mg od.

The primary purpose of the analyses described in this SAP is the evaluation of relevant outcomes in COMPASS that occurred during the LTOLE part of the study.

Hence, this SAP is to be read in conjunction with the study protocol and the SAPs mentioned above. The COMPASS study will be concluded with the completion of LTOLE.

## 2. Study Objectives

### Objective for Long-Term Open-Label Extension

- The objective of LTOLE is to make rivaroxaban 2.5 mg bid + aspirin 100 mg od available to COMPASS trial subjects until the treatment is commercially available or for approximately 3 years from regulatory approval of LTOLE in a country, whichever comes first.

[figure not shown]
### **3. Study Design**

For the general study design, please refer to integrated SAP, version 4.1.

LTOLE will provide open-label rivaroxaban 2.5 mg bid plus aspirin 100 mg od to COMPASS subjects until it is commercially available or for approximately 3 years from regulatory approval of LTOLE in a country, which ever comes first.

Not all sites who participated in COMPASS also participated in LTOLE. For subjects participating in COMPASS, the follow-up before LTOLE depends on the treatment group: follow-up for the antithrombotic portion ended in 2017 (release data of first clean database 04 AUG 2017), and follow up of pantoprazole/placebo randomization ended in 2018 (relase date of second clean data base 21 SEP 2018). First Patient First Visit for COMPASS LTOLE was achieved on 09 JAN 2018. Hence, patients who had not been randomized to pantoprazole/placebo have not been followed up during the time from close-out of the antithrombotic portion of the trial until they entered LTOLE. On the other hand, subjects randomized to pantoprazole/placebo may have had their final pantoprazole/placebo follow-up visit with or after LTOLE initiation visit. Hence, these subjects have been followed-up continuously.

LTOLE will involve an initiation visit and a follow-up period with follow-up visits every 6 months. The follow-up will be concluded with a final follow-up visit at the end of the study.

#### 4. General Statistical Considerations

Please also refer to integrated SAP, version 4.1.

During LTOLE, no outcome events are planned to undergo an event adjudication process as was done during the initial part of the study and all events will be analyzed as reported by the investigators. Please refer to Section 6.1 for the arrangement of events during LTOLE and before LTOLE initiation.

